If the participant died and the death date is complete (ie, not partial date) and before the imputed last study date, the complete death date should be used as the imputed last study date.

23) The precision in reporting numerical values should be as follows:

Raw measurements will be reported the same as the data captured electronically or on the CRF.

Standard deviation and standard error will be reported to one more significant decimal place than the raw measurement.

Mean, median, minimum, Q1, Q3, maximum, 95% CIs will be reported to the same number of decimal places of the raw measurements.

Exceptions may be considered; for example, if more than 4 significant digits are provided for the measurement.

24) Duration of HIV Diagnosis (years) is defined as the year from the First Dose Date/Study Day 1 Date minus the year of HIV diagnosis from Disease Under Study (HIV) CRF page.

25) Duration of HIV Treatment (Years) is defined as the year from the First Dose Date/Study Day1 Date minus the year first started HIV treatment from Disease Under Study (HIV) CRF page.

SAP-Final-GS-US-380-4580

ELECTRONIC SIGNATURES

Signed by	Meaning of Signature	Server Date (dd-MMM- yyyy hh:mm:ss)
PPD	Project Team Leader eSigned	17-Nov-2020 00:48:44
PPD	Biostatistics eSigned	17-Nov-2020 21:06:18

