6.2. Pretreatment Assessments

6.2.1. Screening Visit

Participants will be screened within 30 days before Day 1 to determine eligibility for participation in the study. The following will be performed and documented at screening:

- Obtain written informed consent(s)
- Obtain demographic information, including gender at birth, sexual orientation, and gender identity
- Obtain screening number in IWRS
- Obtain medical history including history of HIV-1 disease-related events, and prior medications within 30 days of the screening visit
- If available, obtain documentation of historical genotype(s) (**not required for entry to study**)
- Complete physical examination (urogenital/anorectal exams will be performed at the discretion of the Investigator)
- 12-lead ECG performed supine
- Height
- Vital signs measurement (blood pressure, pulse, respiration rate, and temperature), including weight
- Obtain blood and urine samples as described in Sections [6.9.1](#) and [6.9.2](#)
- Review concomitant medications
- Record any SAEs and all AEs related to protocol mandated procedures occurring after signing of the consent form

Participants meeting all of the inclusion criteria, and none of the exclusion criteria, will return to the clinic within 30 days after screening for the Day 1 Visit. Participants randomized to Treatment Group 1 must continue to take their prior treatment regimen up until the day before their scheduled Day 1 visit. Participants randomized to Treatment Group 2 will continue to take their prior treatment regimen until they switch to FDC of B/F/TAF at Week 24.

From the time of obtaining informed consent through the first administration of study treatment, record all SAEs, as well as any AEs related to protocol-mandated procedures on the adverse events eCRF. All other untoward medical occurrences observed during the screening period, including exacerbation or changes in medical history are to be captured on the medical history eCRF. See Section 7 Adverse Events and Toxicity Management for additional details.

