4. SUBJECT DISPOSITION

4.1. Subject Enrollment and Disposition

4.1.1. Subject Enrollment

The number and percentage of participants randomized at each investigator site will be summarized by treatment group (B/F/TAF and Delayed Switch to B/F/TAF) and overall using the B/F/TAF safety analysis set. The denominator for this calculation will be the number of participants in the B/F/TAF safety analysis set. Similarly, the number and percentage of participants enrolled in each randomization stratum will be summarized based on reclassified strata using the baseline third agent ARV class based on the Non-Study ARV Medication eCRF.

If there are discrepancies between IWRS and collected data with regard to stratum assignment, a listing of the discrepancies will be provided.

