- 8) Please note, “Not Permitted”, “Unknown”, or missing categories will be excluded from percentage calculation. Except for Mode of infection (HIV Risk Factors), where “Unknown” will be included for percentage calculation, since a participant may fit more than 1 HIV risk factors, therefore percentage may add to more than 100% and no p-value will be generated.
- 9) Defining Baseline ARV Medication

Baseline ARV Medication

All participants are expected to enter the study on an ARV regimen other than FDC of B/F/TAF that consists of any two NRTIs + allowed 3rd agent for ≥ 6 months (see Protocol Section 4.2 for allowed agents)

Using the ARV raw dataset, for the B/F/TAF treatment group, include all prior and/or current ARVs (ARV.INGRED where ARV.CMSCAT = “Prior ARV” or “Current ARV”), taken on or up to 4 days prior to first dose date as defined in Section 3.8.1 (or randomization date if not treated). For the SBR treatment group, include all prior and/or current ARVs (ARV.INGRED where ARV.CMSCAT = “Prior ARV” or “Current ARV”) taken on Study Day 1.

Use the following rules to determine if the ARV medication is taken on Day 1:

- If ARV end date is before B/F/TAF first dose date -4 for B/F/TAF participants or Day 1 date for SBR participants then exclude. If “Ongoing” is not marked and the end date is completely missing, then exclude. See below for imputation rules for any partial dates of uncertainty.
- If ARV start date is after B/F/TAF first dose date for B/F/TAF participants (or Day 1 visit date for SBR participants) then exclude. See below for imputation rules for any partial dates of uncertainty.

The different categories used for the baseline ARV medication are (1) backbone, (2) third agent, and (3) third agent class.

- For participants with more than one baseline ARV medication record, concatenate the records together using “+” to get one record for each participant. For all ingredients, replace “_” or “+” with “/”.
- For each participant, search for the NRTIs: FTC, TAD, TDF, ABC, AZT, and 3TC. There should be 2 NRTIs for each participant. Create the backbone variable by concatenating the 2 NRTIs listed in the order above and separate by a “/” as per the backbone column in the table below.

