DTG/ABC/3TC	ABC/3TC	DTG	INSTI	DTG + ABC/3TC
DTG/FTC/TAF	FTC/TAF	DTG	INSTI	DTG + FTC/TAF
DTG/FTC/TDF	FTC/TDF	DTG	INSTI	DTG + FTC/TDF
DTG/RPV*	-	DTG and RPV	DTG is INSTI RPV is NNRTI	DTG and RPV
EFV/3TC/TDF	TDF/3TC	EFV	NNRTI	EFV + TDF/3TC
EFV/ABC/3TC	ABC/3TC	EFV	NNRTI	EFV + ABC/3TC
EFV/AZT/3TC	AZT/3TC	EFV	NNRTI	EFV + AZT/3TC
EFV/FTC/TAF	FTC/TAF	EFV	NNRTI	EFV + FTC/TAF
EFV FTC/TDF	FTC/TDF	EFV	NNRTI	EFV + FTC/TDF
ETR/ABC/3TC*	ABC/3TC	ETR	NNRTI	ETR + ABC/3TC
EVG/COBI/FTC/TAF	FTC/TAF	EVG/co	INSTI	EVG/co + FTC/TAF
EVG/COBI/FTC/TDF	FTC/TDF	EVG/co	INSTI	EVG/co + FTC/TDF
FTC/RPV/TAF	FTC/TAF	RPV	NNRTI	RPV + FTC/TAF
FTC/RPV/TDF	FTC/TDF	RPV	NNRTI	RPV + FTC/TDF
LPV/RTV/FTC/TDF	FTC/TDF	LPV/RTV	PI	LPV/r + FTC/TDF
MVC/FTC/TDF	FTC/TDF	MVC	CCR5	MVC + FTC/TDF
NFV/FTC/TAF	FTC/TAF	NFV	PI	NFV + FTC/TAF
NVP/AZT/3TC	AZT/3TC	NVP	NNRTI	NVP + AZT/3TC
NVP/FTC/TDF	FTC/TDF	NVP	NNRTI	NVP + FTC/TDF
NVP/FTC/TAF	FTC/TAF	NVP	NNRTI	NVP + FTC/TAF
RAL/ABC/3TC	ABC/3TC	RAL	INSTI	RAL + ABC/3TC
RAL/FTC/TAF	FTC/TAF	RAL	INSTI	RAL + FTC/TAF
RAL/FTC/TDF	FTC/TDF	RAL	INSTI	RAL + FTC/TDF
RTV/DRV/ABC/3TC	ABC/3TC	DRV/r	PI	DRV/r + ABC/3TC
RTV/DRV/FTC/TAF	FTC/TAF	DRV/r	PI	DRV/r + FTC/TAF
RTV/DRV/FTC/TDF	FTC/TDF	DRV/r	PI	DRV/r + FTC/TDF
RTV/RAL*	-	RAL/r	INSTI	RAL/r
TAF/COBI/DRV/FTC	FTC/TAF	DRV/co	PI	DRV/co + FTC/TAF
TAF/DTG/FTC	FTC/TAF	DTG	INSTI	DTG + FTC/TAF

*Protocol Violation

Duration of Baseline ARV Medication

Duration of the baseline ARV medication (defined above) prior/ to the first dose date is defined as (End Date - Start Date+1). Duration will be expressed in years so that duration in days will be divided by 365.25 days.

End date is defined as the first dose date -1 or randomization date if randomized but not dosed.

Start Date: The start date of the baseline ARV medication is the latest start date of all the individual baseline ARV medications selected above

Use the following rules to handle any incomplete start dates

- If only month and year are available, day will be first imputed as 15th, then imputed as the minimum of (the start date of the ARV, first dose date-1, the stop date of the same ARV)
- If only year is available, month and day will be first imputed as July 1st of the year, then imputed as the minimum of (the start date of the ARV, first dose date-1, the stop date of the same ARV)
- No imputation applied for date missing completely

Use the following rules to handle any incomplete stop dates

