- If only month and year are available, day will be first imputed as 15th, then imputed as minimum of (the first dose date-1, the stop date of the ARV)
- If only year is available, month and day will be first imputed July 1st of the year, then imputed as minimum of (first dose date-1, the stop date of the ARV)
- No imputation applied for date missing completely

10) Efficacy analyses:

The 95% CI for percentage estimate of HIV-1 RNA < 50 copies/mL or > 50 copies/mL for each treatment is calculated based on the Clopper-Pearson exact method.

```
proc freq;  
by trt;  
tables event/ binomial;  
exact binomial;  
run;
```

Listing for US FDA-defined snapshot outcome:

In addition to flagging the values of HIV-1 RNA < 50 or \geq 50 copies/mL for virologic outcomes, flag the last available HIV-1 RNA value while on treatment for the following categories:

HIV-1 RNA > 50 copies/mL - Discontinued Study Drug Due to AE or Death and
Last Available HIV-1 RNA > 50 copies/mL

HIV-1 RNA > 50 copies/mL - Discontinued Study Drug Due to Other reason* and
Last Available HIV-1 RNA > 50 copies/mL

No virologic Data Discontinued Study Drug Due to AE or Death and Last Available HIV-1 RNA < 50 copies/mL

No virologic Data Discontinued Study Drug Due to Other reason* and Last Available HIV-1 RNA < 50 copies/mL

Note:* Other reasons include participants who discontinued study drug due to investigator's discretion, subject decision, lost to follow-up, noncompliance with study drug, protocol violation, pregnancy, and study terminated by sponsor.

11) TEAE

Events with Missing Onset Day and/or Month

An event is considered treatment emergent if the following 3 criteria are met:

- i. The month and year (or year) of onset date is the same as or after the month and year (or year) of the first dose of study drug, and
- ii. The month and year (or year) of the onset date is the same as or before the month and year (or year) of the 30th day after the date of the last dose of study drug, and
- iii. End date is as follows:

The (complete) end date is on or after the first dose date, or

The month and year (or year) of end date is the same or after the month and year (or year) of the first dose of study drug, or

End date is completely missing

Events with Completely Missing Onset Date

An AE with a completely missing onset date is defined as TEAE if end date meets any of the criteria specified in 3) above.

12) Toxicity Grades:

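### SAP Appendix 6 can drop a baseline antiretroviral with a partial stop date in the immediate-switch group, because the imputed date can fall before the four-day window

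*SAP*

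**What the plan says.** Item 9 of SAP Appendix 6 builds the baseline regimen from the antiretroviral records. For the B/F/TAF group it takes drugs "taken on or up to 4 days prior to first dose date as defined in Section 3.8.1". The operative exclusion is "If ARV end date is before B/F/TAF first dose date -4 for B/F/TAF participants or Day 1 date for SBR participants then exclude". It then adds "See below for imputation rules for any partial dates of uncertainty".

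The only stop-date rules below that point come at the end of the item, after the definition of regimen duration:

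- Month and year known: "If only month and year are available, day will be first imputed as 15th, then imputed as minimum of (the first dose date-1", with the drug's own stop date as the other term of the minimum.
- Year known: "If only year is available, month and day will be first imputed July 1st of the year, then imputed as minimum of" the same two terms.
- Date completely missing: no imputation.

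On actual use, Protocol Section 6.2.1 says that participants randomized to Treatment Group 1 "must continue to take their prior treatment regimen up until the day before their scheduled Day 1 visit".

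The derived regimen feeds the baseline regimen tables (SAP Section 5.2), the enrolment summary by "reclassified strata using the baseline third agent ARV class based on the Non-Study ARV Medication eCRF" with its listing of discrepancies against IWRS (SAP Section 4.1.1), and the renal and fasting-metabolic subgroups by baseline drug (SAP Sections 3.4.2, 7.2.3 and 7.2.5.1).

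**The concern.** The exclusion rule needs the stop date to within a few days. The imputation rule supplies a mid-month or mid-year date, and the cap at first dose minus 1 can only pull that date back. Nothing rescues a record whose known month or year is fully compatible with use up to the switch. For example, with a stop recorded as June and a first dose on 28 June, the imputed stop is 15 June. The cut-off is 24 June, so the drug is dropped, although the protocol expects it to have been taken through 27 June.

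Elsewhere the SAP resolves partial dates the other way. For adverse events (Section 7.1.5.2) and concomitant medications (Section 7.4.2), a record counts when its known month and year are compatible with the treatment period.

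At stake is a correct description of what participants switched from: backbone, third agent and third-agent class.

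**Working it through.** **Do the stop-date rules govern selection?** They are printed under the duration heading, but duration does not use the imputed stop as its end point: "End date is defined as the first dose date -1 or randomization date if randomized but not dosed". The imputed stop enters duration only as a cap on an imputed start date. The selection step refers forward to these rules, so they apply to it.

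**Inputs.** F is the first B/F/TAF dose date. The cut-off is F − 4 (SAP Appendix 6 item 9). The true stop is assumed to be F − 1 (Protocol Section 6.2.1). The plan states no figure of its own to reproduce.

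**Month and year known.** Imputed stop S = min(15th of the stop month, F − 1). The record is dropped if S < F − 4. Let D be the day of the month of F.

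- D from 2 to 15: S = F − 1, kept.
- D from 16 up: S = the 15th, dropped if 15 < D − 4, that is D ≥ 20. Day 19 compares 15 with 15 and is kept; day 20 compares 15 with 16 and is dropped.
- D = 1: the stop lies in the previous month, so S is the 15th of that month, while F − 4 is the 25th or later. Dropped.

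Count in a 365-day year:

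- Day 20 or later: 7 × 12 + 4 × 11 + 9 = 137.
- Day 1: 12.
- Total: 149, and 149/365 = 40.8%.

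**Year only.** S = min(1 July of the stop year, F − 1).

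- First dose 5 July: S = 1 July, cut-off 1 July, kept.
- First dose 6 July: S = 1 July, cut-off 2 July, dropped, and so on to 31 December: 26 + 31 + 30 + 31 + 30 + 31 = 179 dates.
- First dose 1 January: the stop lies in the previous year, so S is 1 July of that year. Dropped: 1 date.
- Total: 180, and 180/365 = 49.3%.

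A day-by-day enumeration gave the same counts for 2019, and 150 and 180 of 366 for 2020.

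**Delayed-switch group.** These thresholds do not carry over, because item 9 compares that group's end dates with the Day 1 date. If that is the randomized Day 1 visit and the switch comes 168 days later, no month-and-year record is lost. Year-only records are lost only for a Day 1 from 2 to 17 July (16 dates).

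**Check of the alternative.** With S = min(last day of the stop month, F − 1), or min(31 December of the stop year, F − 1), a true stop at F − 1 always gives S = F − 1. Wrongful exclusions: 0 of 365 for either type of partial date.

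**The case against.** The strongest reply is that the situation may hardly arise. The switch takes place at a site visit, and Protocol Section 6.4 has the first dose observed, or confirmed by phone if the old regimen was taken that morning. This is therefore the stop date a site is least likely to lack. Partial dates are more plausible for older drugs, which should be excluded. Protocol Section 9.1.6 provides for data queries. The regimen table in SAP Appendix 6, drawn from the data, leaves the backbone blank in only two rows, both marked as protocol violations, and no row lacks a third agent. Item 9 expects two NRTIs and a third agent for everyone, so a gap would be visible. Section 6.2.1 is also an instruction, not a record of what each participant took.

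Most of this stands as a limit on frequency. It does not make the rule correct. The table gives example rows, so it cannot show that no record was lost, and visibility helps only if someone acts on it.

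The reply has most force for year-only dates. Eligibility requires at least six months on the current regimen, so an earlier drug can share the first-dose year mainly when that dose falls in the second half of the year. There, exclusion may be right.

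A reader might also infer that affected participants lose their whole regimen and land in the subgroups defined by not containing TAF or TDF, EFV, or RPV, DTG, RTV or cobicistat. The documents do not support that as stated. Exclusion works record by record, so the whole regimen goes only if it is one record or every component has a partial date. No section says where a participant with an empty or incomplete regimen is placed.

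**Conclusion.** The defect is real but minor. Read literally, item 9 wrongly drops a month-and-year record on 40.8% of possible first-dose dates and a year-only record on 49.3%. Those shares are conditional on a partial stop date in the immediate-switch group, a true stop on the day before first dose, and first doses spread evenly over the year. Complete dates and records marked ongoing are untouched.

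It is tempting to apply these percentages to the 320 planned participants. That is not possible: the documents do not give the number of partial stop dates, and it may be zero.

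The outputs exposed are descriptive: the baseline-regimen and stratum tables, the stratum discrepancy listing and, depending on how gaps are handled, the renal and fasting-metabolic subgroups. Efficacy is not affected. The final analysis does not repeat the primary and secondary endpoints, and SAP Section 3.4.1 plans no efficacy subgroups.

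**What to change.** Add a stop-date rule to item 9 that applies only to the selection of baseline drugs, leaving the duration calculation as it is:

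- **Month and year known:** impute the last day of that month, capped at first dose date minus 1.
- **Year only:** impute 31 December, capped at first dose date minus 1, only if the record is marked 'Current ARV' or no replacement drug of the same class starts before the first dose. Otherwise keep the existing rule and query the site.

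The cost is a short addition to the programming specification and a rerun of the derivation. The small downside is that a drug truly stopped earlier in its recorded month could occasionally be retained. It would then show as an extra NRTI or third agent and could be reviewed. If the specification cannot be changed, list the immediate-switch participants whose derived regimen is empty or incomplete and check them against the Non-Study ARV Medication eCRF.

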8.6.3. Laboratory Evaluations

Selected laboratory data (using conventional units) will be summarized using only observed data. Absolute values and changes from baseline at all scheduled visits will be summarized.

Graded laboratory abnormalities will be defined using the grading scheme defined in Grading of laboratory abnormalities attached in [Appendix 4](#).

Incidence of treatment-emergent laboratory abnormalities, defined as values that increase at least 1 toxicity grade from baseline at any time post baseline up to and including the date of last dose of study treatment plus 30 days, will be summarized by treatment. If baseline data are missing, then any graded abnormality (ie, at least a Grade 1) will be considered treatment emergent. The maximum post baseline toxicity grade will be summarized by laboratory parameter.

Laboratory abnormalities that occur before the first dose of study treatment or after the last dose of study treatment plus 30 days will be included in a data listing.

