AST (SGOT)	1.25 to 2.50 × ULN	> 2.50 to 5.00 × ULN	> 5.00 to 10.00 × ULN	> 10.00 × ULN
ALT (SGPT)	1.25 to 2.50 × ULN	> 2.50 to 5.00 × ULN	> 5.00 to 10.00 × ULN	> 10.00 × ULN
GGT	1.25 to 2.50 × ULN	> 2.50 to 5.00 × ULN	> 5.00 to 10.00 × ULN	> 10.00 × ULN
Alkaline Phosphatase	1.25 to 2.50 × ULN	> 2.50 to 5.00 × ULN	> 5.00 to 10.00 × ULN	> 10.00 × ULN
Total Amylase	> 1.0 to 1.5 × ULN	> 1.5 to 2.0 × ULN	> 2.0 to 5.0 × ULN	> 5.0 × ULN
Pancreatic Amylase	> 1.0 to 1.5 × ULN	> 1.5 to 2.0 × ULN	> 2.0 to 5.0 × ULN	> 5.0 × ULN
Lipase	> 1.0 to 1.5 × ULN	> 1.5 to 3.0 × ULN	> 3.0 to 5.0 × ULN	> 5.0 × ULN
Albumin Pediatrics <16 years	-	2.0 to < LLN g/dL 20 to < LLN g/L	< 2.0 g/dL < 20 g/L	NA
	3.0 g/dL to < LLN 30 g/L to < LLN	2.0 to < 3.0 g/dL 20 to < 30 g/L	< 2.0 g/dL < 20 g/L	NA
≥ 16 years				

URINALYSIS				
	Grade 1	Grade 2	Grade 3	Grade 4
Hematuria (Dipstick)	1+	2+	3-4+	NA
Hematuria (Quantitative) See Note below				
Females	>ULN - 10 RBC/HPF	> 10-75 RBC/HPF	> 75 RBC/HPF	NA
Males	6-10 RBC/HPF	> 10-75 RBC/HPF	> 75 RBC/HPF	NA
Proteinuria (Dipstick)	1+	2-3+	4+	NA
Proteinuria, 24 Hour Collection				
Adult and Pediatric ≥ 10 Years	200 to 999 mg/24 h	>999 to 1999 mg/24 h	>1999 to 3500 mg/24 h	> 3500 mg/24 h
Pediatric > 3 Mo to < 10 Years	201 to 499 mg/m ² /24 h	>499 to 799 mg/m ² /24 h	>799 to 1000 mg/m ² /24 h	> 1000 mg/ m ² /24 h
Glycosuria (Dipstick)	1+	2-3+	4+	NA

Notes:

- Toxicity grades for Quantitative and Dipstick Hematuria will be assigned by Covance Laboratory, however for other laboratories, toxicity grades will only be assigned to Dipstick Hematuria.
- With the exception of lipid tests, any graded laboratory test with a result that is between the LLN and ULN should be assigned Grade 0.
- If the severity of a clinical AE could fall under either one of two grades (eg, the severity of an AE could be either Grade 2 or Grade 3), select the higher of the two grades for the AE.

CARDIOVASCULAR				
	Grade 1	Grade 2	Grade 3	Grade 4
Cardiac Arrhythmia (general) (By ECG or physical exam)	Asymptomatic AND No intervention indicated	Asymptomatic AND Non-urgent medical intervention indicated	Symptomatic, non-life-threatening AND Non-urgent medical intervention indicated	Life-threatening arrhythmia OR Urgent intervention indicated
Cardiac-ischemia/Infarction	NA	NA	Symptomatic ischemia (stable angina) OR Testing consistent with ischemia	Unstable angina OR Acute myocardial infarction

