7.2.2.2. Summaries of Laboratory Abnormalities

The following summaries (number and percentage of participants) for treatment-emergent laboratory abnormalities will be provided by lab test and treatment group (B/F/TAF, Delayed Switch to B/F/TAF, and All B/F/TAF); participants will be categorized according to the most severe postbaseline abnormality grade for a given lab test:

- Treatment-emergent laboratory abnormalities
- Treatment-emergent Grade 3 and 4 laboratory abnormalities

For all summaries of laboratory abnormalities, the denominator is the number of participants with any nonmissing postbaseline values for the particular laboratory test.

A by-subject listing of all treatment-emergent laboratory abnormalities and treatment-emergent Grade 3 or 4 laboratory abnormalities will be provided by subject ID number and visit in chronological order.

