7.2.5.2. Proteinuria by Urinalysis (Dipstick)

The proteinuria by urinalysis (dipstick) toxicity grade (Grade 0 to Grade 3) will be summarized by baseline proteinuria toxicity grade and treatment group (B/F/TAF and Delayed Switch to B/F/TAF) by visit. In addition, the last on-treatment proteinuria toxicity grade will be summarized by baseline proteinuria toxicity grade and treatment group. On-treatment data is as all data collected up to 1 day after permanent discontinuation of study drug.

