7.8. Changes from Protocol-Specified Safety Analyses

No changes from the protocol-specified safety analyses are planned.

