For toxicity grade summaries, include post-baseline graded results as defined in Section 7.2.2.1, not just those used in by-visit summaries.

13) Graded Laboratory Abnormalities Summary

The following labels will be used for treatment-emergent laboratory abnormalities and treatment-emergent Grade 3 or 4 laboratory abnormalities summary tables and listings:

Battery	Lab Test Label Used in l-labtox Listing	Toxicity Direction	Lab Test Label Used in t-labtox Table
Hematology	Hemoglobin	Decrease	Hemoglobin (Decreased)
	Neutrophils	Decrease	Neutrophils (Decreased)
	Platelets	Decrease	Platelets (Decreased)
	WBC	Decrease	WBC (Decreased)
Chemistry	Albumin	Decrease	Albumin (Decreased)
	Alkaline Phosphatase	Increase	Alkaline Phosphatase (Increased)
	ALT	Increase	ALT (Increased)
	Amylase	Increase	Amylase (Increased)
	AST	Increase	AST (Increased)
	Bicarbonate	Decrease	Bicarbonate (Decreased)
	Corrected Calcium	Increase	Corrected Calcium (Hypercalcemia)
	Corrected Calcium	Decrease	Corrected Calcium (Hypocalcemia)
	Creatine Kinase (CK)	Increase	Creatine Kinase (Increased)
	Creatinine	Increase	Creatinine (Increased)
	Lipase	Increase	Lipase (Increased)
	Magnesium	Decrease	Magnesium (Hypomagnesemia)
	Phosphate	Decrease	Phosphate (Hypophosphatemia)
	Serum Glucose (Fasting)	Increase	Serum Glucose (Fasting, Hyperglycemia)
	Serum Glucose (Fasting)	Decrease	Serum Glucose (Fasting, Hypoglycemia)
	Serum Glucose (Nonfasting)	Increase	Serum Glucose (Nonfasting, Hyperglycemia)
	Serum Glucose (Nonfasting)	Decrease	Serum Glucose (Nonfasting, Hypoglycemia)
	Serum Potassium	Increase	Serum Potassium (Hyperkalemia)
	Serum Potassium	Decrease	Serum Potassium (Hypokalemia)
	Serum Sodium	Increase	Serum Sodium (Hypernatremia)
	Serum Sodium	Decrease	Serum Sodium (Hyponatremia)
	Total Bilirubin	Increase	Total Bilirubin (Hyperbilirubinemia)
	Total Cholesterol (Fasting)	Increase	Total Cholesterol (Fasting, Hypercholesterolemia)
	Triglycerides (Fasting)	Increase	Triglycerides (Fasting, Increased)
LDL (Fasting)	Increase	LDL (Fasting, Increased)	
Urea Nitrogen (BUN)	Increase	Urea Nitrogen (Increased)	
Urinalysis	Urine Blood (Dipstick)	Increase	Urine RBC (Hematuria, Quantitative or Dipstick)*
	Urine Glucose	Increase	Urine Glucose (Glycosuria)
	Urine RBC (Quantitative)	Increase	Urine RBC (Hematuria, Quantitative or Dipstick)*

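### The final-analysis SAP tabulates proteinuria only as shifts at each visit and at the last on-treatment value; the any-time treatment-emergent incidence and worst grade in protocol 8.6.3 are not planned for it

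*SAP*

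**What the plan says.** **Protocol 8.6.3** makes two commitments for graded laboratory data. The first is "Incidence of treatment-emergent laboratory abnormalities, defined as values that increase at least 1 toxicity grade from baseline at any time post baseline", up to last dose plus 30 days, by treatment. The second is "The maximum post baseline toxicity grade will be summarized by laboratory parameter".

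**Protocol Appendix 4** grades dipstick proteinuria: 1+ is Grade 1, 2-3+ is Grade 2 and 4+ is Grade 3. Protocol 6.9.2 and Appendix 2 schedule urinalysis at every visit.

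**SAP 7.2.2.2** carries out the protocol commitment for B/F/TAF, Delayed Switch and All B/F/TAF: "participants will be categorized according to the most severe postbaseline abnormality grade for a given lab test".

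**SAP Appendix 6, item 13** then specifies the tests: "The following labels will be used for treatment-emergent laboratory abnormalities and treatment-emergent Grade 3 or 4 laboratory abnormalities summary tables and listings". The Urinalysis block holds Urine Blood (Dipstick), Urine Glucose and Urine RBC (Quantitative). A note under the table says that INR and PT are graded and listed but kept out of the summary table. There is no such note for urine protein.

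**SAP 7.2.5.2** covers proteinuria separately: "The proteinuria by urinalysis (dipstick) toxicity grade (Grade 0 to Grade 3) will be summarized by baseline proteinuria toxicity grade and treatment group", by visit, for B/F/TAF and Delayed Switch. In addition, "the last on-treatment proteinuria toxicity grade will be summarized by baseline proteinuria toxicity grade and treatment group", using data up to 1 day after permanent discontinuation.

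**SAP 7.8**: "No changes from the protocol-specified safety analyses are planned".

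**The concern.** The protocol's safety summary for a graded test is a per-participant count over the whole treatment period: how many rose by at least one grade, and how far each went. As item 13 stands, hematuria and glycosuria receive that summary and proteinuria does not. The SAP treats proteinuria as a renal evaluation with its own subsection, yet plans only cross-sectional views of it.

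The two kinds of table answer different questions. A participant with 2+ protein at Week 12 and none later appears in the Week 12 table and is Grade 0 in the last-value table. A participant with 1+ at four visits appears in four visit tables. A reader of the study report could not work back from these tables to the number of participants who developed proteinuria on B/F/TAF, or to the distribution of worst grades.

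The treatment-emergent laboratory table for HIV/HBV-coinfected participants (SAP 8.1) would have the same gap if it uses the same labels.

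**Working it through.** The plan states no figure for proteinuria, so there is nothing to reproduce. The check compares texts, followed by an illustration of what the shift tables leave undetermined.

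**Step 1. Is proteinuria the only routine graded test without a row?** I compared the tests scheduled in protocol 6.9.1 and 6.9.2, and graded in Appendix 4 for HIV-positive adults, with item 13.
- Hematology: hemoglobin, neutrophils, platelets and WBC all have rows. Graded lymphocyte and CD4 counts apply only to HIV-negative persons.
- Chemistry: every graded analyte has a row. So do amylase, calcium, magnesium and phosphate, which are not collected after Day 1 (protocol Appendix 2, note n).
- Fasting lipids and glucose: graded tests have rows.
- Urinalysis: blood, RBC and glucose have rows. Protein does not.

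Proteinuria is therefore the only graded test scheduled at every visit that is missing.

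**Step 2. What does SAP 7.2.5.2 supply against protocol 8.6.3?**

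| Item | Protocol 8.6.3 / SAP 7.2.2.2 | SAP 7.2.5.2 |
|---|---|---|
| Grade against baseline at each visit | not the purpose | yes |
| Participants with any rise of at least 1 grade | yes | no |
| Worst post-baseline grade per participant | yes | no; worst within a visit window only |
| Data cutoff | last dose + 30 days | last-value table stops at + 1 day |
| All B/F/TAF column | yes | no |

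**Step 3. Can the any-time count be recovered from the visit tables?** No, it can only be bounded. With n_j participants above their baseline grade at visit j, the number ever affected lies between max(n_j), if the same people are affected every time, and the sum of n_j, if no one is affected twice. If visits were independent with rate p at each of k visits, the expected number is N × [1 − (1 − p)^k].

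The inputs are the planned group sizes (320 and 160). I count 7 post-baseline visits for B/F/TAF (Weeks 4, 12, 24, 36, 48, 60, 72) and 5 for Delayed Switch (study Weeks 28, 36, 48, 60, 72). The visit rates of 2%, 5% and 10% are assumptions; the documents give none.

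| Group | p per visit | Fully persistent: N × p | No overlap: N × p × k | Independent |
|---|---|---|---|---|
| B/F/TAF, N=320, k=7 | 2% | 6.4 | 44.8 | 42.2 (13.2%) |
| | 5% | 16 | 112 | 96.5 (30.2%) |
| | 10% | 32 | 224 | 166.9 (52.2%) |
| Delayed Switch, N=160, k=5 | 2% | 3.2 | 16 | 15.4 (9.6%) |
| | 5% | 8 | 40 | 36.2 (22.6%) |
| | 10% | 16 | 80 | 65.5 (41.0%) |

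**Step 4. Comparison with the last-value table.** With a constant visit rate, that table shows about p. Under full persistence the ratio of ever-affected to last-value is 1. Under independence it is 13.2/2 = 6.6 and 30.2/5 = 6.0 for B/F/TAF, and 9.6/2 = 4.8 and 22.6/5 = 4.5 for Delayed Switch, at 2% and 5% respectively. Independence means no tendency for proteinuria to persist in the same person, so these ratios mark an extreme and are not an estimate. Seven visits is also a maximum, because the extension after Week 48 is optional and ends when the participant has access to the drug.

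**The case against.** **A reader might infer that proteinuria on B/F/TAF is never reported.** The documents do not support that. SAP 7.2.5.2 tabulates grade against baseline grade at every visit. SAP 3.8.3 takes the most conservative categorical result in a window, so transient proteinuria is counted in its own visit table and missed only by the last-value table. SAP 7.2 flags urinalysis results of Grade 1 or higher in by-subject listings. Under protocol 7.5, an abnormality that needs intervention or leads to interruption of study drug is recorded as an adverse event. This SAP also covers only the final analysis. The Week 24 and Week 48 analyses were done earlier, their plans are not among the documents, and they may have tabulated treatment-emergent proteinuria. They could not, however, supply the cumulative count through Week 72.

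**Item 13 could be read as a list of labels, not as an exclusion rule.** SAP 7.2.2.2 promises summaries by test without excluding proteinuria, and the SAP says so explicitly when it withholds a test (INR, PT). This reading is fair, but it does not remove the defect. On it, proteinuria belongs in the tables and has no label; on the other, it has been left out without being declared. Either way item 13 needs the row.

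**A table row may have been lost when the PDF was read.** This cannot be excluded, although the rest of the list looks intact.

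**Importance.** It is tempting to cite the nephrotoxicity section, protocol 7.6.5. That section works from creatinine-based eGFR, repeat creatinine, cystatin C and general evidence of acute renal failure. It does not mention proteinuria and lends no support here. The added table would also be descriptive and uncontrolled, because the final analysis does not summarize the SBR group's first 24 weeks (SAP 2.2).

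**Conclusion.** The point holds in a limited form. For the final analysis, proteinuria is reported only through visit and last-value shift tables. The any-time incidence to last dose plus 30 days, the worst post-baseline grade and the All B/F/TAF column are not planned for it. That departs from protocol 8.6.3, while SAP 7.8 declares no departure. By-subject listings do not replace an incidence.

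The size cannot be fixed from the documents. It runs from no understatement, if proteinuria is fully persistent, to several-fold against the last-value table, if it is intermittent. A definite multiple such as six- or seven-fold should not be claimed: it needs assumed visit rates, complete independence between visits, all seven visits, and comparison with the last-value table alone while ignoring the visit tables.

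The conclusion assumes that the item 13 table is complete as read. It is a minor correction to the reporting of one safety parameter and does not affect the efficacy analyses.

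**What to change.** Add one row to the Urinalysis block of SAP Appendix 6, item 13: `Urine Protein | Increase | Urine Protein (Proteinuria)`. Dipstick proteinuria then enters the treatment-emergent and Grade 3-4 tables and listings of SAP 7.2.2.2 for B/F/TAF, Delayed Switch and All B/F/TAF, with the worst-grade rule and 30-day cutoff used for the other tests. Keep the shift tables of 7.2.5.2, which show persistence and direction of change.

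The cost is one row in an existing table program. No new data are needed. If the omission was intended, SAP 7.8 should instead state that the shift tables replace the protocol's incidence for this test, and why.
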